4 STUDY DESIGN AND RATIONALE

[figure not shown]
4.1 Overview of Study Design

This randomized, observer-blind, active comparator-controlled Phase 3 study will be conducted at multiple sites. The composition of the Quadrivalent VLP Influenza Vaccine to be used in this study includes a mix of recombinant H1, H3, and two B hemagglutinin proteins expressed as VLPs (see Investigational Product Management Manual) and will be based on the 2018-2019 recommended WHO strains for vaccination. The composition of the active comparator is also based on the 2018-2019 recommended WHO strains for vaccination.

Approximately 12,120 non-institutionalized male and female subjects 65 years of age and older with no acute or evolving medical problems will be randomized in a 1:1 ratio into one of two parallel treatment groups, such that approximately 6060 subjects will receive the Quadrivalent VLP Influenza Vaccine at a dose of 30 μ g/strain and approximately 6060 subjects will receive an active comparator. Within the two treatment groups, subjects will be randomized by age into two strata (65 to 74 years of age and 75 years of age and older) in a 2:1 ratio.

A basic outline of the study design is presented in Figure 1.

Medicago R&D Inc. Page 34 of 90

- * Subset of 420 subjects for CMI and humoral assessments
- † AEs will be collected up to Day 21; SAEs, AEs leading to withdrawal, and NOCDs will be collected through to the end of the study.
- ‡ The duration of the surveillance period may be adjusted, based on the observed epidemiology during the season.

Figure 1 Flowchart of Study Procedures

Subjects will participate in this study for approximately eight to ten months, during which a first visit will be scheduled on Day 0 for screening and vaccine administration; subjects will be instructed on how to record reactions, adverse events (AEs), concomitant medication use, and respiratory illness symptoms in their diary and memory aid, as applicable. A phone contact will be made on Days 1 and 8, specifically for review of the subject's safety and concomitant medication data. A visit to the investigator site will occur on Day 21 for a subset of 420 subjects from pre-defined sites in North America (210 subjects per treatment group) for serology sampling and immunogenicity assessments (CMI, HI, MN, and SRH). A final phone contact will be made for a safety assessment at approximately the end of April 2019 (the end of the surveillance period; however, the duration of the surveillance period may be adjusted, based on the observed epidemiology during the season in participating countries).

[figure not shown]
Active and passive surveillance will be conducted from Day 14 until approximately the end of April 2019 (end of the surveillance period). For passive surveillance, subjects will be instructed to report symptoms meeting the definition of a new or worsening respiratory illness and ILI. For active surveillance, subjects will be contacted at least once per week and asked about symptoms of a new or worsening respiratory illness and ILI. The frequency of active surveillance contacts will vary slightly with region:

• North America and Europe: Prior to the start of the influenza season (the start of influenza season will be determined by Medicago through local epidemiology and clinical experience), subjects will be contacted at least once per week, using the contact method most likely to be successful (e.g. subject's preferred method [phone, text, e-mail]). During the influenza season, subjects will be contacted a minimum of two times per week; at least one of these weekly contacts will be through a scripted telephone call, with the remaining contacts via the method most likely to be successful;

Medicago R&D Inc. Page 35 of 90

• Asia: Since there generally is no clearly defined influenza season, contacts will be made a minimum of two times per week, with at least one of these weekly contacts through a scripted telephone call and the remaining contacts via the method most likely to be successful (e.g. subject's preferred method [phone, text, e-mail]).

Reports of respiratory illness will be followed up for the collection of information regarding symptoms, concomitant medication use, and disease burden and the collection of two nasopharyngeal swabs. For subjects in North America and Europe, swabs will only be collected for cases of respiratory illness that occur after the start of the influenza season (as determined by Medicago through local epidemiology and clinical experience); for subjects in Asia, swabs will be collected for any cases of respiratory illness reported during the surveillance period (Day 14 and onwards). Figure 2 outlines the process to be followed for reports of respiratory illness.

^{*} One or more of the following symptoms that persist(s) for or reoccur(s) after a period of at least 12 hours: sneezing, stuffy or runny nose (nasal congestion), sore throat, cough, sputum production, wheezing, and difficulty breathing

Figure 2 Flowchart of Process of Respiratory Illness Report

Throughout the influenza season, the number of laboratory-confirmed influenza cases will be reviewed periodically by selected members of Medicago and the CRO who will be independent of study conduct and analysis. In the event of an insufficient attack rate of confirmed influenza (minimum of 198 cases), the study will be either continued or extended into another season to enrol more subjects and a protocol amendment will be issued to address changes to the enrolment plan.

Medicago R&D Inc. Page 36 of 90

[†] The planned active surveillance will continue and will include questions on the respiratory illness progression until the final 30 (+ 7) day follow-up for the illness.

[‡] Data past Day 30 of onset of respiratory illness is not to be collected

^{*}A visit for NP swab collection should be done for any subject who reports any respiratory illness as per regional specifications: after the start of the local influenza season (subjects in North America and Europe) or for any respiratory illness reported during the surveillance period (i.e. Day 14 onwards; subjects in Asia).

^{\$\Pi\$} Swabs must be collected within preferably 24 hours after reporting of symptoms and prior to the use of influenza antiviral treatment medication. If swabs cannot be collected within 36 hours after reporting of the respiratory symptoms, this will be reported as a deviation; however NP swabs should still be collected if the subject still has at least one respiratory illness symptom.

4.2 Rationale of Study Design

4.2.1 Randomization

Randomization will be used to minimize bias in the assignment of subjects to treatment groups, to increase the likelihood that known and unknown subject attributes (e.g. demographic and baseline characteristics) are evenly balanced across treatment groups, and to enhance the validity of statistical comparisons across treatment groups.

4.2.2 Observer-blinding

Observer-blinded treatment will be used to reduce potential bias during data collection and evaluation of the clinical endpoints.

4.2.3 Age Group Stratification

Since age can affect the immune response, subjects will be randomized into each treatment group by age in two strata (65 to 74 years of age and 75 years of age and older) in a 2:1 ratio in order to ensure a representative age distribution within each treatment group.

4.2.4 Dose Selection

The dose of $30 \mu g$ /strain was selected based on data from previous studies as the lowest dose to consistently meet the historical CBER criteria and the dose most comparable with the most commonly used commercial licensed vaccines.

4.2.5 Active Comparator Selection

The active comparators (FluLaval® Tetra/Quadrivalent and/or Fluarix® Tetra/Quadrivalent (all produced and/or distributed by GlaxoSmithKline Inc) were selected on the basis that these products are approved quadrivalent influenza vaccines and represent the most widely used dose in elderly subjects. In addition, these products have been well-studied and have well-established immunogenicity, efficacy, and safety profiles for this population.

4.2.6 Study Duration

The duration of this study will be approximately eight to ten months post-vaccination for all subjects in order to capture the maximal number of cases of influenza caused by vaccinematched strains in a single influenza season.

4.2.7 Efficacy Assessments

The efficacy endpoint for this study (ie: sequential reverse transcription polymerase chain reaction [RT-PCR] and serotyping to define influenza types/subtypes) is standard to demonstrate influenza VE. The regional differences in the timing of NP swab collection (for cases of respiratory illness that occur after the start of the influenza season for subjects in North America and Europe) was included in order to minimize unpleasant study procedures that would have

Medicago R&D Inc. Page 37 of 90

minimal benefit [i.e. prior to influenza season] and to maximize subject compliance during peak influenza season in these regions with well-defined influenza seasons.

5 STUDY POPULATION

5.1 Inclusion Criteria

Subjects must meet all of the following inclusion criteria to be eligible for participation in this study; no protocol waivers are allowed:

- 1. Subjects must have read, understood, and signed the informed consent form (ICF) prior to participating in the study; subjects must also complete study-related procedures and communicate with the study staff at visits and by phone during the study;
- 2. Subject must have a body mass index (BMI) \leq 35 kg/m²;
- 3. Subjects are considered by the Investigator to be reliable and likely to cooperate with the assessment procedures and be available for the duration of the study;
- 4. Male and female subjects must be 65 years of age and older at the Screening/Vaccination visit (Visit 1);
- 5. Subjects must be non-institutionalized (e.g. not living in rehabilitation centres or old-age homes; living in an elderly community is acceptable) and have no acute or evolving medical problems prior to study participation and no clinically relevant abnormalities that could jeopardize subject safety or interfere with study assessments, as assessed by the Principal Investigator or sub-Investigator (thereafter referred as Investigator) and determined by medical history, physical examination, and vital signs;

Note: Subjects with a pre-existing chronic disease will be allowed to participate if the disease is stable and, according to the Investigator's judgment, the condition is unlikely to confound the results of the study or pose additional risk to the subject by participating in the study. Stable disease is generally defined as no new onset or exacerbation of pre-existing chronic disease three months prior to vaccination. Based on the Investigator's judgment, a subject with more recent stabilization of a disease could also be eligible.

5.2 Exclusion Criteria

Subjects who meet any of the following criteria will be excluded from participating in this study; no protocol waivers are allowed:

- 1. According to the Investigator's opinion, history of an ongoing acute or evolving medical or neuropsychiatric illness. 'Evolving' is defined as:
 - Requiring a new medical or surgical treatment during the three months prior to study vaccine administration unless the criteria outlined in inclusion criterion no. 5 can be met (i.e. the Investigator can justify inclusion based upon the innocuous nature of medical/surgical events and/or treatments);
 - Requiring any significant change in a chronic medication (i.e. drug, dose, frequency) during the three months prior to study vaccine administration due to uncontrolled symptoms or drug toxicity unless the innocuous nature of the medication change meets

Medicago R&D Inc. Page 38 of 90

the criteria outlined in inclusion criterion no. 5 and is appropriately justified by the Investigator.

- 2. Any medical or neuropsychiatric condition or any history of excessive alcohol use or drug abuse that would render the subject unable to provide informed consent or unable to provide valid safety observations and reporting, including methadone (methadone as treatment for opioid dependence may be acceptable if the subject has been otherwise opioid-free for at least three years);
- 3. Any autoimmune disease other than hypothyroidism on stable replacement therapy (including, but not limited to rheumatoid arthritis, systemic lupus erythematosus, Crohn's disease, type 1 diabetes, and inflammatory bowel disease) or any confirmed or suspected immunosuppressive condition or immunodeficiency including known or suspected human immunodeficiency virus (HIV), Hepatitis B or C infection, the presence of lymphoproliferative disease;
- 4. Any history of status asthmaticus or ongoing serious problems with asthma, hospitalization for asthma control, or recurrent asthma episodes requiring medical attention in the last three years (one or more episodes per year);
- 5. Administration or planned administration of any non-influenza vaccine within 30 days prior to randomization up to blood sampling on Day 21. Immunization on an emergency basis will be evaluated case-by-case by the Investigator;
- 6. Administration of any adjuvanted or investigational influenza vaccine within one year prior to randomization or planned administration prior to the completion of the study;
- 7. Administration of any 'standard', non-adjuvanted influenza vaccine (e.g. live attenuated trivalent/quadrivalent inactivated influenza vaccine or split trivalent/quadrivalent inactivated influenza vaccine administered by intranasal, intradermal, or intramuscular [IM] route) within six months prior to randomization and up to completion of the study;
- 8. Use of any investigational or non-registered product within 30 days or five half-lives, whichever is longer, prior to randomization or planned use during the study period. Subjects may not participate in any other investigational or marketed drug study while participating in this study until after the study;
- 9. Treatment with systemic glucocorticoids at a dose exceeding 10 mg of prednisone (or equivalent) per day for more than seven consecutive days or for ten or more days in total, within one month of study vaccine administration; any other cytotoxic or immunosuppressant drug, or any immunoglobulin preparation within three months of vaccination and until the completion of the study. Low doses of nasal or inhaled glucocorticoids are allowed. Topical steroids are permitted;
- 10. Any significant disorder of coagulation including, but not limited to, treatment with warfarin derivatives or heparin. Persons receiving prophylactic anti-platelet medications (e.g. low-dose aspirin [no more than 100 mg/day]), and without a clinically apparent bleeding tendency are eligible. Subjects treated with new generation drugs that do not increase the risk of IM bleeding (e.g. clopidogrel) are also eligible;
- 11. History of allergy to any of the constituents of the Quadrivalent VLP Influenza Vaccine, any components of the active comparator quadrivalent vaccine, or tobacco;

Medicago R&D Inc. Page 39 of 90

- 12. History of anaphylactic allergic reactions to plants or plants components (including fruits and nuts);
- 13. Use of antihistamines within 48 hours prior to study vaccination;
- 14. Daily use of large doses of medication for pain control or inflammation (e.g. opioids, nonsteroidal anti-inflammatory drugs [NSAIDs]). Use of a singular regular dose either in the morning or at bedtime would not be exclusionary;
- 15. Use of prophylactic medications (e.g. acetaminophen/paracetamol, aspirin, naproxen, or ibuprofen) within 24 hours of randomization to prevent or pre-empt symptoms due to vaccination;
- 16. Planned use of influenza antiviral treatment medication before the collection of NP swabs (e.g. oseltamivir, zanamivir, rapivab);
- 17. Have a rash, dermatological condition, tattoos, muscle mass, or any other abnormalities at the injection site that may interfere with injection site reaction rating;
- 18. Subjects who have received a blood transfusion within 90 days prior to study vaccination;
- 19. Subjects with abnormal vital signs (systolic blood pressure [BP] \geq 150 mmHg and/or diastolic BP \geq 95 mmHg for individuals taking antihypertensive medication and \geq 140 mmHg and/or diastolic BP \geq 90 mmHg for individuals not taking antihypertensive medication; heart rate [HR] \leq 45 beats/min and \geq 100 beats/min) evaluated by an Investigator to be clinically significant. A subject with abnormal vital signs results may be included in the study based on Investigator's judgment (e.g. a resting HR \leq 45 in highly trained athletes);
- 20. Presence of any febrile illness (including an oral temperature [OT] ≥ 38.0 °C within 24 hours prior to vaccination;
- 21. Cancer or treatment for cancer within three years prior to study vaccine administration. Persons with a history of cancer who are disease-free without treatment for three years or more are eligible. However, individuals with conditions such as treated and uncomplicated basal cell carcinoma of the skin or non-treated, non-disseminated local prostate cancer may be eligible;
- 22. Subjects identified as an Investigator or employee of the Investigator or clinical site with direct involvement in the proposed study, or identified as an immediate family member (i.e. parent, spouse) of the Investigator or any employee of Medicago (or their family members);
- 23. Subjects with a history of Guillain-Barré Syndrome.

5.3 Prior and Concomitant Therapy

New or changed medications reported by the subject post-vaccination and through to the end of the study will be recorded in the source documents and transcribed in the electronic case report form (eCRF) as a concomitant medication as per the conditions outlined in the next paragraph. Since AEs may be secondary to new medications, the Investigator will explore the reasons for the change or for the new medication intake and document these AEs, if any.

Concomitant medications must be reported in the eCRF (reason for use, dates of administration, dosage, and route) if the use meets the following conditions:

Medicago R&D Inc. Page 40 of 90

- Within 30 days preceding vaccination: any treatments and/or medications specifically
 contraindicated (e.g. influenza vaccines, any immunoglobulins or other blood products, or
 any immune modifying drugs, etc.);
- From randomization to Day 21, inclusive: any medication (including, but not limited to, over-the-counter medicines such as aspirin or antacids), vitamins, and mineral supplements;
- From Day 22 to the end of the study, inclusive: any concomitant medication(s) administered to treat a NOCD (see Section 13.1.4 for definition of NOCD), SAE, or AE leading to withdrawal; any concomitant medication used to treat an AE that occurred before Day 21 and that is still being used afterwards (i.e. ongoing use); and any concomitant medications used to treat a protocol-defined respiratory illness or ILI;
- Any vaccine not foreseen in the study protocol.

Please refer to the eCRF completion guidelines for details of data entry requirements.

5.4 Prohibited Therapy

Please refer to Section 5.2 (exclusion criteria numbers 3, 4, 6, 7, 8, 9, 10, 13, 15, 16, and 21) for details on medications or therapies prohibited prior to randomization, prior to NP swab collection, and/or during the conduct of this study.

Given that an important objective of this study is to evaluate the tolerability of the study vaccine, the use of prophylactic medications to prevent or pre-empt symptoms due to vaccination is specifically prohibited up to Day 7 (end of collection of solicited symptoms). A prophylactic medication is a medication administered in the absence of ANY symptom and in anticipation of a reaction to the vaccination (e.g. an antipyretic is considered to be prophylactic when it is given in the absence of fever or any other symptoms, to prevent fever from occurring, vitamins used to boost immune system, etc.).

The use of influenza antiviral treatment (e.g. oseltamivir, zanamivir, rapivab) is not permitted until the NP swabs are collected.

6 TREATMENT ALLOCATION AND BLINDING

6.1 Randomization

Potential study subjects will be screened and assigned a subject number. Once all screening procedures, including Day 0 pre-randomization procedures, have been completed and the study eligibility is confirmed by the Investigator, the randomization numbers will be allocated to subjects within the appropriate treatment group by the randomization system.

Subjects will be randomized to one of two treatment groups, based on a computer-generated randomization schedule prepared by or under the supervision of Medicago before the study. Prior to randomization into the two treatment groups, subjects will be stratified by age into two groups (65 to 74 years of age and 75 years of age and older) and enrolled in a 2:1 ratio.

Medicago R&D Inc. Page 41 of 90

Once a randomization number has been assigned, it will not be re-used for any reason. No subjects will be randomized into the study more than once. If a randomization number is allocated incorrectly, no attempt will be made to remedy the error once the study vaccine has been dispensed: the subject will continue on the study with the assigned randomization number and associated treatment. The study staff will notify the Sponsor Contact as soon as the error is discovered without disclosing the study vaccine administered. Admission of subsequent eligible subjects will continue using the next unallocated number in the sequence.

The randomization number and treatment will be recorded along with the six-digit subject number for each subject in the investigational product accountability log. The Investigator will not be provided with randomization codes, but it will be possible to unblind the treatment in an emergency situation.

6.2 Blinding

This is an observer-blind study: the subjects, the Investigators, and those responsible for study endpoint evaluations or review or analysis of the study data will not have access to the randomization codes. Any code break will be documented and reported to Medicago (or its designee) in a timely manner. In a medical emergency, the Investigator may unblind the treatment for that subject without prior consultation with the Sponsor. In such an event, the Investigator will need to contact the responsible Medical Officer as soon as possible after the unblinding to discuss the case.

Since there will be differences in the VLP vaccine and the active comparator preparations (e.g. multi-dose vial versus single-dose syringe, possibly physical appearance), the site staff involved in the preparation and administration of the treatments will not be involved in any activity that could introduce a bias, such as the evaluations of respiratory symptoms, ILI, AEs, or reactogenicity of the subjects following vaccination.

This study is blinded through to the end of the surveillance period of the last subject. The randomization code, will not be available during the course of the study to any investigator or any person directly involved in the clinical conduct of the study (including data cleaning and data analysis) except the independent team from the contract research organization (CRO) and selected individuals from Medicago. The selected individuals will be independent of study conduct and analysis and will review the number of influenza cases to allow for discussion of the clinical data and critical business decisions (e.g. extension of recruitment for another season) prior to study completion. It is anticipated that approximately five people from Medicago and the CRO will have access to the number of cases in a unblinded manner. Also, the central laboratories and the staff at the clinical site (except the staff involved in the preparation/administration of the study vaccine, the quality assurance auditor, and the quality control reviewers) will remain blinded throughout the entire study duration.

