12.2 Sample Size Determination

The sample size of approximately 12,120 subjects (6060 subjects per treatment group) was selected to have 80 % power to determine non-inferiority, based on the assumption of 20 % VE, a 2 % or greater attack rate in the active comparator (ARV_C) for protocol-defined ILI caused by any influenza viral types/subtypes, and a 10 % dropout rate. Non-inferiority will be concluded if the lower bound of the two-sided 95 % CI is greater than -20 %.

In the event of an insufficient attack rate of confirmed influenza (minimum of 198 cases), the study will be either continued or extended into another season to enrol more subjects and a protocol amendment will be issued to address changes to the enrolment plan.

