Reports of respiratory illness will be followed up for the collection of information regarding symptoms, concomitant medication use, and disease burden and the collection of two nasopharyngeal (NP) swabs. For subjects in North America and Europe, swabs will only be collected for cases of respiratory illness that occur after the start of the influenza season (as determined by Medicago through local epidemiology and clinical experience); for subjects in Asia, swabs will be collected for any cases of respiratory illness reported during the surveillance period (Day 14 and onwards). Figure 2 outlines the process to be followed for reports of respiratory illness.

^{*} One or more of the following symptoms that persist(s) for or reoccur(s) after a period of at least 12 hours: sneezing, stuffy or runny nose (nasal congestion), sore throat, cough, sputum production, wheezing, and difficulty breathing

Figure 2 Flowchart of Process of Respiratory Illness Report

Throughout the influenza season, the number of laboratory-confirmed influenza cases will be reviewed periodically by selected members of Medicago and the CRO who will be independent of study conduct and analysis. In the event of an insufficient attack rate of confirmed influenza (minimum of 198 cases), the study will be either continued or extended into another season to enroll more subjects and a protocol amendment will be issued to address changes to the enrolment plan.

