3.7.2. Blinding

Observer-blinded treatment will be used to reduce potential bias during data collection and evaluation of the clinical endpoints.

This is an observer-blind study: the subjects, the Investigators, and those responsible for study endpoint evaluations or review or analysis of the study data will not have access to the randomization codes. Any code break will be documented and reported to Medicago (or its designee) in a timely manner. In a medical emergency, the Investigator may unblind the treatment for that subject without prior consultation with the Sponsor. In such an event, the Investigator will need to contact the responsible Medical Officer as soon as possible after the unblinding to discuss the case.

Since there will be differences in the VLP vaccine and the active comparator preparations (e.g. possibly physical appearance), the site staff involved in the preparation and administration of the treatments will not be involved in any activity that could introduce a bias, such as the evaluations

of respiratory symptoms, ILI, AEs, or local or systemic reactions developed by the subjects following vaccination.

This study is blinded through to the end of the surveillance period of the last subject. The randomization code, will not be available during the course of the study to any investigator or any person directly involved in the clinical conduct of the study (including data cleaning and data analysis) except the independent team from the contract research organization (CRO) and selected individuals from Medicago. The selected individuals will be independent of study conduct and analysis and will review the number of influenza cases to allow for discussion of the clinical data and critical business decisions (e.g. extension of recruitment for another season) prior to study completion. It is anticipated that approximately five people from Medicago and the CRO will have access to the number of cases in an unblinded manner. Also, the central laboratories and the staff at the clinical site (except the staff involved in the preparation/administration of the study vaccine, the quality assurance auditor, and the quality control reviewers) will remain blinded throughout the entire study duration.

Blinding measures will be applied to maintain the observer-blindness of the blinded staff and to allow identification of the study treatment only by staff involved in the preparation/administration of the study vaccine/active comparator.

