10.8. Other Safety

No other safety assessments are planned for this study.

Statistical Analysis Plan Sponsor: Medicago; Protocol No.: CP-PRO-QVLP-014

INTERIM ANALYSES 11.

No interim analysis is scheduled.

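### The extension trigger is a pooled count that needs no randomization code, yet about five sponsor and CRO people get unblinded case numbers for that decision and no sentence keeps the arm split out of it

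*Protocol*

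**What the plan says.** **The trigger.** Protocol 12.2 says that with an "insufficient attack rate of confirmed influenza (minimum of 198 cases), the study will be either continued or extended into another season", with a protocol amendment to follow. The same figure stands in the protocol synopsis, Protocol 4.1, and SAP 3.4 and 3.6. None of these places gives a threshold by arm.

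**The review.** Protocol 4.1 says that "the number of laboratory-confirmed influenza cases will be reviewed periodically by selected members of Medicago and the CRO". SAP 3.4 repeats this.

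**The access.** Protocol 6.2 exempts an independent CRO team and selected sponsor individuals from the restriction on the randomization code. It says that "approximately five people from Medicago and the CRO will have access to the number of cases in a unblinded manner". The purposes are discussion of the clinical data and "critical business decisions (e.g. extension of recruitment for another season) prior to study completion". SAP 3.7.2 agrees that these people "will have access to the number of cases in an unblinded manner".

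**The safeguards.** Protocol 6.2 states: "The selected individuals will be independent of study conduct and analysis". Any change to the protocol needs a formal amendment (Protocol 17.1), which goes to the regulatory authorities (Protocol 17.2.1). The SAP is to be final before unblinding and database lock (Protocol 12.3).

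**The analysis.** SAP Section 11 reads: "No interim analysis is scheduled". SAP 8.2.1 makes no multiplicity adjustment for the primary endpoint. SAP 8.2 and 8.2.2 conclude non-inferiority from an ordinary two-sided 95% score interval.

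**The concern.** A pooled count tells the sponsor how much information has accrued. A count by arm, with equal allocation, tells it how the primary comparison is going. The stated rule needs the first, and the plan supplies the second to people who take part in the extension decision.

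Independence from conduct and analysis limits leakage to sites and analysts. It does not keep the split out of the extension decision, which is the purpose given for the access. The text also leaves room for judgement: the study may be continued or extended, the review is periodic, and the business decisions are given only by example.

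Two things are at stake. If the split influences the choice, the unadjusted 95% CI no longer carries a 2.5% one-sided error. Even if it does not, the sponsor has no sentence to cite when asked whether it did.

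A secondary point is what counts as a case. The 198 follows an assumption about ILI attack rates in the synopsis and Protocol 12.2. Protocol 10.2.1, however, treats any positive RT-PCR as a laboratory-confirmed case, and swabs are triggered by any respiratory illness, including sneezing or a runny nose alone. The trigger could therefore be read as counting cases outside the primary endpoint.

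**Working it through.** **Inputs from the documents** (Protocol 12.2, 4.1; SAP 3.6, 8.2): 12,120 subjects allocated 1:1; comparator attack rate 2.0%; relative VE 20%, so 1.6% on VLP; dropout 10%; non-inferiority if the lower 95% limit for VE exceeds −20%, that is, an upper limit for RR below 1.2.

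**1. Where 198 comes from.** Expected total cases = evaluable subjects per arm × (2.0% + 1.6%).
- Dropout as 12,120 / 1.1 / 2 = 5,509 per arm: 5,509 × 0.036 = 198.3.
- Dropout as 6,060 × 0.9 = 5,454 per arm: 5,454 × 0.036 = 196.3.

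The first convention gives the plan's figure and the second comes within 2. Either way 198 is a total over both arms at the primary-endpoint rates, and counting to it needs no treatment code. The steps below use 5,509 per arm.

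**2. What the split would show.** Non-inferiority is met when the score statistic for RR = 1.2 exceeds 1.96: Z = (1.2·p_C − p_V) / SE, with the SE computed under RR = 1.2, to match the SAP's score interval. The largest VLP count that meets it is:

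| Pooled cases | VLP | Comparator |
|---|---|---|
| 150 | 69 | 81 |
| 197 | 93 | 104 |

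Anyone holding the split can see whether the primary criterion is already met.

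**3. One-sided error at the boundary RR = 1.2, by how the decision is taken.** There were 1,000,000 simulated trials per row. A second season of the same size and rates is assumed, as are comparator rates below 2.0%. The pooled rule extends whenever the total is below 198. Assumption A keeps that trigger but skips the extension when non-inferiority is already met.

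| Comparator rate | Chance of <198 cases | Pooled rule | Assumption A |
|---|---|---|---|
| 1.5% | 88% | 2.5% | 4.0% |
| 1.6% | 61% | 2.5% | 3.5% |
| 1.7% | 28% | 2.5% | 3.0% |
| 1.8% | 8% | 2.6% | 2.7% |
| 2.0% | 0.1% | 2.5% | 2.5% |

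**4. Assumption B: extension because non-inferiority was missed, whatever the count.** With k the added information as a fraction of the first stage, and Z1, Z2 independent standard normals at the boundary, Zc = (Z1 + √k·Z2) / √(1 + k). The error is P(Z1 > 1.96 or Zc > 1.96):
- k = 0.25: 3.5%
- k = 0.5: 3.8%
- k = 1: 4.2%

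A separate check with a log-RR interval, 5,454 per arm and comparator rates of 0.8%, 1.2% and 1.6% gave about 2.5% for the pooled rule and 3.6% to 4.1% for the rule in Assumption A.

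**5. Which cases count.** Suppose exactly 198 RT-PCR positives are counted and 10% to 20% of them are not ILI (an assumption; the documents give no share). Primary cases are then 198 × 0.9 = 178 to 198 × 0.8 = 158. Simulated power at RR = 0.8 is 82% with 198 primary cases, 78% with 178 and 73% with 158.

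**The case against.** The strongest reply is that the written rule is sound. It is mandatory, makes no reference to arm, and leaves the error rate at 2.5% to 2.6% if followed. Both inflation scenarios depart from it: A skips an extension the text says will happen, and B extends for a reason no section provides. At the planned 2.0% comparator rate, A adds nothing. The reviewers are declared independent, and any extension would pass through an amendment seen by ethics committees and regulators.

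Most of this stands as a limit on size. The plan's own rule contains no error, and the figures describe what discretion could do, not what the sponsor intends. It does not answer the point itself. An amendment shows that an extension happened, not why. The rule bites only when the attack rate is low, which is where the inflation appears. And Protocol 6.2 grants the unblinded access expressly for the extension decision.

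On the case definition, the objection is that the protocol's ILI is broad, so the non-ILI share may be smaller than 10%; that 198 is a minimum; and that its position after the ILI assumption suggests the intended reading. All fair. That point is a clarification and carries less weight than the access question.

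**Conclusion.** The concern holds and should be fixed. By-arm access is not needed for the stated rule, and no sentence excludes the split from the decision. Followed mechanically, the pooled rule costs nothing in error. If the split is used, one-sided error could rise from 2.5% to about 4%, and the size depends on three assumptions: that the split influences the choice, that the comparator attack rate falls below the planned 2.0% (for Assumption A), and how much information the extension adds. The risk that is certain is to credibility: an extended trial with an unadjusted interval, and a plan that cannot show the extension was taken blind to the result.

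**What to change.** 1. In Protocol 6.2 and SAP 3.7.2, give the case-review team only the pooled, treatment-blind count, and state that the decision to continue or extend uses only that count. Remove code access for case review. Keep it for preparing the schedule, unblinded drug-accountability monitoring and safety unblinding.
2. If by-arm counts are wanted, place them with an independent committee under a charter, or declare the looks in SAP Section 11 with an alpha adjustment.
3. In Protocol 4.1 and 12.2 and SAP 3.4 and 3.6, state that the 198 counts subjects with RT-PCR-confirmed protocol-defined ILI from Day 14, pooled over arms. Say that per protocol status is provisional in season, because SAP 5.3 settles deviations and the peak period only at the blinded review before lock.

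The cost is wording in these sections and a link between swab result and symptom record for the running count. Sample size, margin, threshold and analysis do not change. The sponsor gives up early by-arm information for business planning.
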